**List of Abbreviations and Definition of Terms**

ADA	Anti-drug antibody
ADCC	Antibody-dependent cellular cytotoxicity
AE	Adverse event
AFP	Alpha-fetoprotein
ALP	Alkaline phosphatase
ALT	Alanine aminotransferase
ANC	Absolute neutrophil counts
aPTT	Activated Partial prothrombin time
AST	Aspartate aminotransferase
ATD	Accelerated titration design
AUC	Area under curve
BOIN	Bayesian optimal interval design
BP	Blood pressure
BUN	Blood urea nitrogen
CBC	Complete blood count
CEA	Carcinoma embryonic antigen
CI	Confidence interval
CR	Complete response
CRF	Case report form
CT	Computerized tomography
CTCAE	Common Terminology Criteria for Adverse Events
DLT	Dose limiting toxicity
ECG	Electrocardiography
ECOG	Eastern Cooperative Oncology Group
EGFR	Epidermal growth factor receptor
FDA	Food and Drug Administration
GCP	Good Clinical Practice
GCP	Good clinical practice
Hb	Hemoglobin
HBcAb	Hepatitis B core antibody
HBeAg	Hepatitis B “e” antigen
HBsAg	Hepatitis B surface antigen
HBV	Hepatitis B virus

HCG	Human chorionic gonadotropin
Hct	Hematocrit
HCV	Hepatitis C virus
HIV	Human immunodeficiency virus
IC50	50% inhibitory concentration
ICF	Informed consent form
ICH	International Conference on Harmonization
IHC	Immunohistochemistry
IND	Investigational new drug application
INR	International normalized ratio
IP	Investigational product
IRB	Institutional review board
IV	Intravenous
KDR	Kinase domain receptor
LDH	Lactate dehydrogenase
LLN	Lower limit of normal
mAb	Monoclonal antibody
MedDRA	Medical Dictionary for Regulatory Activities
MRI	Magnetic resonance imaging
MTD	Maximum tolerated dose
MUGA	Multigated acquisition
NCI	National Cancer Institute
ORR	Overall response rate
OS	Overall survival
PD	Pharmacodynamics
PD	Progressive disease
PFS	Progression free survival
PK	Pharmacokinetics
PO	Per OS
PR	Partial response
PS	Performance status
Q3W	Every three weeks
QD	Once every day
QOL	Quality of Life

QW	Once every week
RBC	Red blood cells
RECIST	Response evaluation criteria in solid tumors
RP2D	Recommended phase 2 dose
SAE	Serious adverse event
SAP	Statistical analysis plan
SD	Stable disease
SRC	Safety review committee
SUSAR	Suspected unexpected serious adverse reaction
TSH	Thyroid-stimulating hormone
ULN	upper limit of normal values
VEGF	Vascular endothelial growth factor
VEGFR2	Vascular endothelial growth factor receptor 2
WBC	White blood cell (counts)
WHODD	World Health Organization Drug Dictionary
WWCBP	Women with child bearing potential

## **SYNOPSIS OF THE STUDY**

### **Title**

A Phase 1 Study of HLX06, a Humanized Monoclonal Antibody Targeting Human Vascular Endothelial Growth Factor Receptor-2 in Patients with Advanced Solid Tumors Refractory to Standard Therapy.

### **Sponsor**

Henlix Biotech Co. LTD

### **Investigational product**

HLX06 recombinant anti-vascular endothelial growth factor receptor 2 (VEGFR2) human IgG1 monoclonal antibody.

### **Study type**

Interventional

### **Study phase**

Phase 1 first-in-human study.

### **Primary objective**

To identify safety and the maximum tolerated dose (MTD) of HLX06 in patients with advanced or metastatic tumors refractory to standard therapy.

### **Secondary objectives**

- The pharmacokinetics of HLX06 at different doses in patients.
- The pharmacodynamics of HLX06 at different doses in patients.
- The immunogenicity of HLX06 in human beings.
- The anti-tumor effects of HLX06 in patients.
- The potential prognostic and predictive biomarkers of HLX06 for advanced solid tumors.

### **Primary outcome measures**

- Numbers and percentage of patients with adverse events (AEs).
- Maximum tolerated dose of HLX06.

### **Secondary outcome measures**

- Maximum concentration ( $C_{\max}$ ) in different cohorts.
- Minimum concentration ( $C_{\min}$ ) in different cohorts.
- Area under concentration ( $AUC_{0-\tau}$ ) in different cohorts.
- Half-life ( $T_{1/2}$ ) of HLX06 in different cohorts.
- Clearance (CL) rate of HLX06 in different cohorts.
- Volume of distribution ( $V_{ss}$ ) at steady state in different cohorts.
- The presence and percentage of anti-HLX06 antibody (immunogenicity).
- Disease control rate.
- Overall response rate.
- Duration of response

## **Eligibility criteria**

### **Inclusion criteria**

- Eligible patients must be 18-years of age or older or per local regulations.
- Patients with histologically-proven measurable or evaluable advanced or metastatic solid tumors who have failed standard therapy or for whom no standard therapy is available. (For patients with hepatocellular carcinoma, the diagnosis needs to be supported by dynamic CT/MRI, if pathological confirmation is not attainable)
- Eastern Cooperative Oncology Group (ECOG) performance status of  $\leq 2$  at the time of study entry.
- Able to provide informed consent.
- A life expectancy longer than three months.
- Adequate hematologic functions, as defined by: absolute neutrophil counts  $\geq 1500/\text{mm}^3$ ; a hemoglobin level  $\geq 10 \text{ gm/dL}$ ; a platelet count  $\geq 100,000/\text{mm}^3$ .
- Adequate hepatic function defined by: a total bilirubin level  $\leq 1.5x$  of upper limit of normal (ULN); aspartate transaminase (AST) and alanine transaminase (ALT) levels  $\leq 2.5 x$  of ULN or  $\leq 5x$  of ULN in known hepatic metastases or with primary hepatocellular carcinoma.
- Adequate renal function, as defined by the creatinine clearance rate  $\geq 50 \text{ mL/minute}$  by Cockcroft-Gault formula.
- Adequate cardiac function defined as left ventricular ejection fraction (LVEF) $\geq 50\%$ .
- Use of effective contraceptive measures if procreative potential exists.

- At least 28 days from prior major surgery, prior cytotoxic chemotherapy, or prior therapy with investigational agents (or medical device) or local radiotherapy before 1st infusion of HLX06.
- For patients with hepatocellular carcinoma, their Child-Pugh score has to be A.
- Able to be followed up as required by the study protocol.

### **Exclusion criteria**

- Patients with large centrally located pulmonary lesions adjacent to or invading large blood vessels.
- Hemoptysis more than  $\frac{1}{2}$  teaspoon (approximately 2-3 mL) of red blood per day.
- Patients who still have  $\geq$  grade 2 toxicities from prior therapies.
- Concurrent unstable or uncontrolled medical conditions with either of the followings:
  - Active systemic infections;
  - Poorly controlled hypertension (systolic blood pressure  $\geq$  160 mmHg or diastolic blood pressure  $\geq$ 100 mmHg), or poor compliance with anti-hypertensive agents;
  - Clinically significant arrhythmia, unstable angina pectoris, congestive heart failure (class III or IV of New York Heart Association [NYHA]) or acute myocardial infarction within 6 months;
  - Uncontrolled diabetes or poor compliance with hypoglycemics;
  - The presence of chronically unhealed wound or ulcers
  - Other chronic diseases, which, in the opinion of the investigator, could compromise safety of the patient or the integrity of study.
- Newly-diagnosed or symptomatic brain metastases (patients with a history of brain metastases must have received definitive surgery or radiotherapy, be clinically stable, and not taking steroids for brain edema). Anticonvulsants are allowed.
- Any concurrent malignancy other than basal cell carcinoma or carcinoma in situ of the cervix. (Patients with a previous malignancy but without evidence of disease for  $\geq$  3 years are allowed to participate).
- Pregnancy (confirmed by serum beta human chorionic gonadotropin [ $\beta$ HCG]) or breast-feeding (for female patients only).
- A known history or clinical evidence of a deep vein or arterial thrombosis, or pulmonary embolism within 6 months of first infusion of HLX06.
- Less than six weeks from last infusion of ramucirumab, or any other anti-VEGF monoclonal antibody therapy (Last treatment with other monoclonal antibodies targeting

proteins other than anti-angiogenic factors is permitted if  $\geq 4$  weeks prior to the first infusion of HLX06).

- Proteinuria  $\geq 2+$  in routine urinalysis (patients with a protein value of  $\leq 500$  mg confirmed by a 24-hour urine collection are eligible).
- Known history of human immunodeficiency virus infection (HIV).
- The patient is the investigator, sub-investigator or any one directly involved in the conduct of the study.

### **Study design**

This study employs the modified accelerated titration design (ATD) 2A[1] and Bayesian optimal interval design (BOIN) to assign patients in the study cohort and identify MTD.

ATD 2A design assumes that the toxicities and effects increase monotonically with doses. It starts with a rapid initial escalation phase by using cohorts of a single new patient to lower the probability of exposing patients to sub-therapeutic doses.[1] When moderate-to-severe toxicities emerge at higher doses, the acceleration phase ends and the study returns to cohorts with 3 new patients.

The BOIN design is a novel adaptive dose-finding method that allows dose escalation and de-escalation and estimates the posterior probability of toxicity rate using updated information [2]. This design is considered to have higher probability of identifying the MTD.

**Dose levels and sample size:** 250, 500, 750, 900, 1200, 1500 mg (flat dose, with no adjustment of body weight or body surface area)[3]. A maximum of 30 patients will be enrolled in the phase 1 study. Patients who withdraw from the study during the first cycle due to reasons not related to treatment-emergent toxicities will be replaced.

Dose escalation sequence is modified from the Fibonacci sequence.

**Determination of starting dose and its dose levels:** the starting dose is **500** mg (flat dose), which is at dose level 2 and approximately equal to 1/6 of human equivalent dose of highest non-severely toxic dose (HNSTD) in the *cynomolgus* study[4].

**Target toxicity rate: 30%**

**Study cycle: Every four weeks.**

**ATD phase and cohort size**

The accelerated phase starts with one new patient per cohort. When the patient does not experience dose-limiting toxicities (defined later) during the first cycle of treatment at the assigned dose level, the next new patient will be assigned to the next higher dose level of HLX06 (*ie. intrapatient dose escalation is NOT allowed*).

When the first instance of first-cycle dose-limiting toxicities (DLTs), or the second instance of first-cycle grade $\geq 2$  toxicities of any types occurs, the acceleration phase stops and the cohort expands to **three** new patients at the current and subsequent dose levels and switch to BOIN design.

### **Dose escalation/de-escalation rule and Bayesian optimal interval design (BOIN)**

After the end of acceleration phase, the decision to escalate or de-escalate in subsequent cohorts is based on the numbers of patients experiencing DLTs and the total number of patients treated at the current dose level (Table 1). The decision to escalate or de-escalate is based by pre-defined safety and toxicity boundary. If the probability of the DLT rate falls below the safety boundary, the dose for the next cohort escalates. By contrast, if the probability of DLTs arises above the toxicity boundary, the dose de-escalates in the next cohort. Otherwise, the dose level stays the same in the next cohort. The enrollment continues until the maximum of 30 patients is reached. The safety boundary in this study is set at 21% (70% of target rate); and the toxicity boundary, at 39%, (130% of target rate), respectively. The detailed rules are described on page 19 . A hypothetical scheme of ATD and BOIN design in the 30 patients is shown in Figure 1.[2]

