**Table 1. Dose escalation table**

No. of patients treated at current dose level	3	6	9	12	15
Escalate if # of DLT	0	1	2	3	3
Remain at the same dose if # of DLT	1	2	3	4	4,5
De-escalate if # of DLT	2	3	4	5	6
Eliminate if # of DLT	3	4	6	7	8

The rules to escalate or de-escalate are as follows:

- (a) “Eliminate” means that we eliminate the current and higher doses from the trial to prevent treating any future patients at these doses because they are overly toxic.
- (b) When we eliminate a dose, we automatically de-escalate the dose to the next lower level. When the lowest dose is eliminated, we stop the trial for safety. In this case, no dose should be selected as the MTD.
- (c) If none of the actions (i.e., escalation, de-escalation or elimination) is triggered, we treat the new patients at the current dose.
- (d) If the current dose is the lowest dose and the rule indicates dose de-escalation, we will treat the new patients at the lowest dose unless the number of DLTs reaches the elimination boundary, at which point we will terminate the trial for safety.
- (e) If the current dose is the highest dose and the rule indicates dose escalation, we will treat the new patients at the highest dose up to maximum 30 patients.
- (f) If the number of new patients treated at the current dose reaches 15, stop the trial and determine the MTD based on data from enrolled patients.

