##### **3.1.1. Accelerated titration design and cohort size**

In the ATD 2A design, the study starts with acceleration phase. In this phase, each cohort consists of one NEW patient for each dose level. After first cycle of treatment, the patient will be evaluated for the toxicities in last cycle. If this patient does not have DLTs, the next patient is allowed to receive the treatment at the next higher dose level.

In the acceleration phase, the newly enrolled patients start at the highest dose level, in which no moderate toxicities are observed in prior patients.

When the first instance of first-cycle DLT or the second instance of first-cycle grade $\geq 2$  toxicities of any types occurs, acceleration phase ends and the cohorts for the current dose level expand to three NEW patients and the study switches the BOIN design phase.

In the acceleration phase, intra-patient dose escalation is NOT allowed.

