##### **3.1.2. Bayesian optimal interval design and rules of dose escalation and de-escalation**

After the acceleration phase, the study uses BOIN design to determine rule of dose escalation and de-escalation. First, the target toxicity rate in this study is set at **30%**, which is the most

common toxicity rate for conventional 3+3 design, indicating that for an oncologic agent, the toxicity rate higher than 30% is NOT desirable[15].

Different from the rule-based 3+3 design, the decision to escalate or de-escalate in BOPIN design is based on the posterior probability of DLTs from updated information. The probability of DLTs is determined by the number of DLTs and the cumulative number of patients treated at the current dose. The safety boundary to escalate the dose is set at 70% of target toxicity rate (i.e. 21%); and the toxicity boundary is, at 130% of target toxicity rate (i.e. 39%), respectively. If the probability of DLTs at the current dose level falls below 21%, the dose in the next cohort escalates to the next higher level. By contrast, when the probability of DLT at the current dose level arises above 39% (130% of target rate), the dose in the next cohort de-escalates to the next lower level. The dose level for the next cohort remains the same if the probability of toxicity is within the safety and toxicity boundary. The enrollment continues until the maximum of 30 patients are reached.

The detailed rule of dose escalation and de-escalation is tabulated in Table 1.

There are also two pre-set EARLY STOPPING RULES in this study.

- Stop the trial if the lowest dose (dose level 1) is eliminated due to overt toxicities.
- Stop the trial and estimate the MTD if the number of new patients treated at the current dose level reaches 15

The detailed statistical methods for dose escalation and de-escalation and estimation of MTD are described in Section 11. This study uses R software and BOPIN package for setting up the specifications. The detailed R codes for this study are described in the Appendix (Section 15.5).

Patients who experience DLTs may be allowed to continue the treatment at the next lower dose level after the toxicities revert to grade $\leq 1$  in 28 days after last infusion, if the Investigator judges that the patient still meet the inclusion criteria and might benefit from continuous treatment.

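### Titration produces totals of 4, 7, 10 or 13 at a dose, which Table 1 does not cover, and the printed 21%/39% thresholds are not the rule behind Table 1

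*Combined protocol and SAP*

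**What the plan says.** The trial opens with one-patient titration cohorts from 500 mg and then moves to BOIN cohorts of three (Synopsis, ATD phase and cohort size; Sections 3.1.1 and 11.1). At the switch the Synopsis calls for three "new patients at the current and subsequent dose levels and switch to BOIN design", and Section 3.1.1 says that "the cohorts for the current dose level expand to three NEW patients".

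From then on the Synopsis bases decisions on the number of DLTs and "the total number of patients treated at the current dose level (Table 1"). Section 3.1.2 agrees: "The probability of DLTs is determined by the number of DLTs and the cumulative number of patients treated at the current dose". Neither leaves out titration patients.

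The decision rule appears in two forms:

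- **Table 1** gives DLT counts for 3, 6, 9, 12 and 15 patients. Rule (c) beneath it adds: "If none of the actions (i.e., escalation, de-escalation or elimination) is triggered, we treat the new patients at the current dose". Rule (f) stops the trial "If the number of new patients treated at the current dose reaches 15".
- **The text** gives thresholds: "The safety boundary in this study is set at 21% (70% of target rate); and the toxicity boundary, at 39" per cent. Section 3.1.2 says that if the DLT probability "falls below 21%, the dose in the next cohort escalates to the next higher level", and Section 3.2 repeats this.

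Section 11.1.2 describes the same 0.21 and 0.39 as an acceptable toxicity range. The R script in Section 15.6 (15.5 in the table of contents) passes them to the BOIN package as p.saf and p.tox.

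**The concern.** There are two defects, and they compound.

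**Table 1 is too short.** Titration leaves one patient on each level from 500 mg up to the switch level. If three patients are added at the switch, that dose holds four straight away. If the switch cohort is three in total, the next de-escalation to a titrated level gives 1 + 3 = 4. Either way, totals of 4, 7, 10 and 13 can arise. Figure 1 is not in the copy available here and may show which switch cohort is meant, but it cannot add columns to Table 1.

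**The text states a different rule.** Where Table 1 is silent, a reader has the 21%/39% thresholds or rule (c). The thresholds are not what generated Table 1. Rule (c), read literally, means staying at the dose for any DLT count at an unlisted total.

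For example, take three in total at the switch, with 0/1 at 500 mg, 0/1 at 750 mg and 2/3 at 900 mg. Table 1 de-escalates to 750 mg. One DLT in three new patients there makes 1/4. The text keeps the next cohort at 750 mg; the BOIN rule sends it back to 900 mg, where two of three patients had DLTs. This choice should be settled before the trial starts.

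**Working it through.** **Inputs.** Target 0.30, p.saf 0.21, p.tox 0.39, cohort size 3 (Section 15.6 script); titration cohort 1 (Synopsis); early stop at 15 on a dose, maximum 30 patients.

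**Step 1: reproduce Table 1.** BOIN boundaries on the observed proportion y/n:

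- λe = ln(0.79/0.70) / ln[(0.30×0.79)/(0.21×0.70)] = 0.2532; escalate if y/n ≤ λe.
- λd = ln(0.70/0.61) / ln[(0.39×0.70)/(0.30×0.61)] = 0.3441; de-escalate if y/n ≥ λd.

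For n = 3, 6, 9, 12 and 15 these give escalate at ≤ 0, 1, 2, 3, 3 and de-escalate at ≥ 2, 3, 4, 5, 6. Every escalate, stay and de-escalate entry matches. Neither 25.3% nor 34.4% is printed in the documents.

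**Step 2: try the text's rule on Table 1.** With escalation below 21% and de-escalation above 39%, 2/9 (22.2%) and 3/12 (25.0%) mean stay, whereas Table 1 escalates at both. Reading probability as a posterior mean, (y+1)/(n+2) with an assumed uniform prior, does worse: it contradicts Table 1 at 1/3 (0.400, de-escalate), 1/6 (0.250, stay), 2/9, 2/12, 3/12 and 3/15.

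**Step 3: the missing totals (observed proportion).**

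| n | BOIN: escalate / de-escalate | Text: escalate / de-escalate | Conflict |
|---|---|---|---|
| 4 | ≤1 / ≥2 | 0 / ≥2 | 1/4 (25.0%): escalate vs stay |
| 7 | ≤1 / ≥3 | ≤1 / ≥3 | none |
| 10 | ≤2 / ≥4 | ≤2 / ≥4 | none |
| 13 | ≤3 / ≥5 | ≤2 / ≥6 | 3/13 (23.1%): escalate vs stay; 5/13 (38.5%): de-escalate vs stay |

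**Step 4: how often 1/4 occurs.** On first return to a titrated dose whose lead-in patient had no DLT, P(1/4) = 3p(1−p)². That is 33%, 44% and 38% at true DLT rates p of 15%, 30% and 50%.

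**Step 5: simulation.** Table 2's six scenarios, 10,000 trials per cell, the same simulated patients under each rule, all patients counted. Titration starts at 500 mg and ends at the first DLT, the second grade ≥2 toxicity, or 1500 mg. Table 1 governs its own columns; the rules differ only at other totals. The trial stops at n ≥ 15 on a dose or 30 patients, and the MTD comes from isotonic regression. Assumed: non-DLT grade ≥2 probability of 10%, 30% or 50%, and an elimination cut-off of 0.96 or 0.97.

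| | Three in total at switch | Three added at switch |
|---|---|---|
| Next dose differs, text vs BOIN (% of trials) | 5 to 40 | 6 to 71 |
| Change in correct selection, text minus BOIN (points) | −0.7 to +1.1 | −2.2 to +1.2 |
| Fewer patients above a 39% true DLT rate under text (per trial) | 0.1 to 0.9 | 0.2 to 2.1 |

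With three in total, 28% to 79% of trials meet an uncovered total (13% to 53% of decisions). Using the text at every count, including 2/9 and 3/12, changes correct selection by −2.6 to +1.1 points and dose allocation in 8% to 49% of trials (three in total).

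**Step 6: elimination.** No cut-off is stated. With a uniform prior assumed, P(p > 0.30) is 0.9527 at 5/9 (kept in Table 1) and 0.9712 at 4/6 (eliminated), so the cut-off lies in that range. At the missing totals, only 3/4 (0.9692) and 7/13 (0.9685) fall inside it and are undetermined.

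**The case against.** The strongest reply is that the method is specified. Several sections send the reader to Table 1, and Sections 11.1 and 15.6 give the package, version and inputs, from which the missing escalate and de-escalate rows follow. Nor does any section offer 21%/39% specifically for unlisted totals. That is right as far as it goes, but the Synopsis and Sections 3.1.2 and 3.2 state those thresholds as the decision rule itself, and Table 1 contradicts them.

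Four further points stand:

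- **The remedy brings no safety gain.** Extending Table 1 makes the return to 900 mg in the example mandatory. The text's rule treats slightly fewer patients at overly toxic doses.
- **5/13 is the weakest conflict.** Table 1 alone places the upper cut-off only between 33.3% and 40%, which 39% fits, and a posterior mean at 5/13 (6/15 = 0.40) would also de-escalate. Agreement at n = 7 and 10 likewise holds only for the observed proportion. The conflicts at 1/4 and 3/13 hold on both readings.
- **The frequencies depend on the scenarios.** Every Table 2 scenario contains a dose with a true DLT rate of at least 45%. With assumed rates of only 5% to 15% at the top dose and three in total, an uncovered total arises in 2% to 21% of trials and the next dose differs in about 0% to 4%. If three are added, uncovered totals always arise and the next dose differs in 10% to 37%.
- **Doses are assigned centrally** (Section 4.4), so sites will not diverge. The sponsor still has to know which rule to apply.

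The literal reading of rule (c) costs far more: correct selection changes by −19.3 to +0.6 points (three in total) or −35.0 to −4.8 (three added). It is probably not intended, and the conclusion does not rest on it.

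**Conclusion.** The concern holds and should be fixed. The contradiction at 2/9 and 3/12 is visible within the protocol and needs no assumption. The gap at 4, 7, 10 and 13 follows from counting all treated patients, whichever switch cohort is meant. The conflicts at 1/4, 3/13 and 5/13 rest on reading probability as the observed DLT proportion.

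The likely effect on MTD selection is modest: about one percentage point with three in total and at most 2.2 with three added (Monte Carlo standard error up to about 0.4). The effect on individual dose assignments is not small under Table 2's scenarios, and it falls soon after the first toxicity signal. Those frequencies depend on the assumed grade ≥2 rates, the elimination cut-off and the scenarios. Table 2 offers no reassurance, because the script's simulation call uses cohorts of three with no titration setting.

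**What to change.** 1. In the Synopsis and Sections 3.1.2 and 3.2, say that 21% and 39% are the BOIN inputs p.saf and p.tox, that the decision boundaries on the observed DLT proportion are 25.3% and 34.4%, and that Table 1 governs.
2. State that titration patients count in both the denominator and the DLT count, and whether two or three patients are added at the switch.
3. Extend Table 1 to every n from 1 to at least 16 using the script's settings, with the Step 3 BOIN rows at n = 4, 7, 10 and 13. Leave the single lead-in patient under the titration rule. Restrict rule (c) to tabulated stay cells.
4. State the elimination cut-off, which settles 3/4 and 7/13.
5. Word the stop as 15 or more, on the same count as the dose decisions, because totals with a lead-in patient go from 13 to 16.

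In adopting the BOIN row at n = 4, the sponsor should knowingly accept that 1/4 escalates. The cost is a larger table and a few sentences in an amendment, with no extra patients or procedures.
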